4.1 Primary Endpoints and Assessment Methods

See Section 9.1 of the protocol.

4.2 Secondary Endpoints and Assessment Methods

See Section 9.2 of the protocol.

4.3 Observational Endpoints and Assessment Methods

See Section 9.3 of the protocol.

4.4 Derived Endpoints: Calculation Methods

4.4.1 Safety

4.4.1.1 Solicited Reactions

4.4.1.1.1 Daily Intensity

All daily records for solicited reactions will be derived into daily intensity according to the following classification: None, Grade 1, Grade 2, Grade 3, or Missing.

For measurable injection site reactions (Erythema/Swelling/Induration/Bruising):

- Grade 1: ≥ 25 to ≤ 50 mm
- Grade 2: ≥ 51 to ≤ 100 mm
- Grade 3: > 100 mm

For measurable systemic reactions (Fever):

- Grade 1: $\geq 38.0^{\circ}\text{C}$ to $\leq 38.4^{\circ}\text{C}$, or $\geq 100.4^{\circ}\text{F}$ to $\leq 101.1^{\circ}\text{F}$
- Grade 2: $\geq 38.5^{\circ}\text{C}$ to $\leq 38.9^{\circ}\text{C}$, or $\geq 101.2^{\circ}\text{F}$ to $\leq 102.0^{\circ}\text{F}$
- Grade 3: $\geq 39.0^{\circ}\text{C}$ or $\geq 102.1^{\circ}\text{F}$

For the derivation of daily intensities the following sequential steps will be applied:

Solicited reactions (except Fever/Pyrexia) with an investigator occurrence recorded as “No” and with all daily records missing then all daily intensities will be derived as “None”.

For non-measurable solicited reactions, daily intensities will correspond to daily records reported in the clinical database. For measurable solicited reactions the daily measurements reported in the clinical database will be converted based upon the intensity scales defined in the protocol; this assumes a reaction that is too large to measure (non-measurable, “NM”) is Grade 3. Note the intensity could be considered “None” (not a reaction) in the analysis despite being considered a reaction by the investigator (eg, swelling measurement > 0 mm but < 25 mm in adults).

Note: The maximum intensity on the ongoing period is derived from the record of the maximum intensity/measurement after the end of the solicited period following the rule described above.

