***Solicited Reaction:***

A solicited reaction is an “expected” AR (sign or symptom) observed and reported under the conditions (nature and onset) prelisted in the protocol and CRB (eg, fever, headache, malaise, myalgia, shivering, or injection site pain, erythema, swelling, induration, or bruising).

By definition, solicited reactions are to be considered as being related to the product administered.

For injectable vaccines, solicited reactions can either be solicited injection site reactions or solicited systemic reactions.

The assessment of these reactions by the investigator is mandatory.

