4.4.1.1.3 Occurrence

Occurrence is derived from the maximum intensity on the period considered:

- None: No occurrence
- Grade 1, Grade 2, or Grade 3: Occurrence
- Missing: Missing occurrence

Subjects with at least one non-missing occurrence for a specific endpoint will be included in the analysis. Conversely, those without a non-missing occurrence will not be included in the analysis of the endpoint.

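### For solicited reactions with no daily records, an investigator's No is analysed but a Yes is dropped; for the subjectively graded reactions this can only leave the rate unchanged or lower it

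*SAP*

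**What the plan says.** SAP 4.4.1.1.1 (Daily Intensity) applies its steps in sequence. The first covers every solicited reaction except fever. Where the investigator's answer is No, the condition and result read "and with all daily records missing then all daily intensities will be derived as", and the value assigned is None.

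The later steps work only from what was recorded day by day. For subjective reactions, "For non-measurable solicited reactions, daily intensities will correspond to daily records reported in the clinical database". For size-based reactions and fever, "For measurable solicited reactions the daily measurements reported in the clinical database will be converted based upon the intensity scales defined in the protocol". No step uses an investigator answer of Yes.

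SAP 4.4.1.1.2 takes the maximum of the daily intensities. SAP 4.4.1.1.3 derives occurrence from that maximum, with the line "Missing: Missing occurrence", and adds: "Conversely, those without a non-missing occurrence will not be included in the analysis of the endpoint".

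Nothing elsewhere in the SAP fills the gap. Section 5.3.1 says that missing safety data are in general not replaced, and 5.3.1.4 sends missing solicited intensities back to 4.4.1.1.1.

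**The concern.** Take two subjects with no daily records for injection site pain. The investigator records No for the first, who enters the denominator as a non-case. The investigator records Yes for the second, who leaves both numerator and denominator. Whether the subject is analysed depends on the outcome being counted.

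The discarded answer is a required record. Protocol 9.2.1.1 says of solicited reactions: "The assessment of these reactions by the investigator is mandatory".

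The handling also differs from the SAP's treatment of unsolicited events. Under SAP 4.4.1.2.1 an unsolicited event counts if it has a verbatim term and is not Grade 0, and under 5.3.1.4 a missing intensity simply stays missing. An unsolicited headache of unknown grade is therefore counted, while a solicited headache of unknown grade that the investigator confirmed is not.

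At stake is the solicited-reaction table, part of the secondary safety objective. Collecting safety data at 60 to 64 years is a stated reason for the trial (Protocol 1.4 and 5.1.2). Protocol 1.3.2.1 lists pain, myalgia, headache and malaise as the very common QIV-HD reactions, so the rule acts on the endpoints with the highest rates.

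**Working it through.** The plan states no figure for this rule, so there is none to reproduce.

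**Step 1: direction for subjectively graded reactions.** Let N be the subjects with either a derived occurrence or a Yes without daily records, x the events found from daily records, and y the subjects with Yes and no daily records.

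- Rate under the SAP: x/(N − y)
- Rate using both answers: (x + y)/N
- Difference: (x + y)/N − x/(N − y) = y(N − y − x)/[N(N − y)]

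Since x cannot exceed N − y, the difference is never negative. It is positive once there is one such subject and at least one analysed non-case.

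Illustration with N = 770 (one vaccine group, SAP Table 3.1) and an assumed x = 300:

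- y = 8: 300/762 = 39.4% under the SAP, against 308/770 = 40.0%.
- y = 15: 300/755 = 39.7% under the SAP, against 315/770 = 40.9%.

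**Step 2: size.** The documents give no share of subjects with blank records, so it is assumed. Let m be the share of subjects with no daily records but with an investigator answer, and p the true rate. Suppose that blank records are unrelated to outcome and that the investigator's answer is accurate. Then

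reported rate = p(1 − m)/[(1 − m) + m(1 − p)] = p(1 − m)/(1 − mp).

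For example, p = 0.40 and m = 0.05 give 0.38/0.98 = 38.78%.

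| True rate | m = 1% | m = 2% | m = 5% | m = 10% |
|---|---|---|---|---|
| 40% | 39.76% (−0.24) | 39.52% (−0.48) | 38.78% (−1.22) | 37.50% (−2.50) |
| 20% | 19.84% (−0.16) | 19.68% (−0.32) | 19.19% (−0.81) | 18.37% (−1.63) |
| 10% | 9.91% (−0.09) | 9.82% (−0.18) | 9.55% (−0.45) | 9.09% (−0.91) |

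Bias in percentage points is in brackets. For scale, the approximate 95% confidence half-width at 40% is 1.96 × √(0.4 × 0.6/770) = 3.5 points per vaccine group, and 4.9 points with the 385 per vaccine group within an age group.

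**Step 3: size-based reactions.** For erythema, swelling, induration and bruising, SAP 4.4.1.1.1 grades anything below 25 mm as None even if the investigator called it a reaction. Let q be the fraction of the y dropped subjects whose reaction truly reached 25 mm. The correct rate is (x + qy)/N, and

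(x + qy)/N − x/(N − y) = y[q(N − y) − x]/[N(N − y)].

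The SAP rate is too low only if q exceeds the observed rate x/(N − y). Protocol 1.3.2.1 puts these reactions at up to 1 in 10, so a downward bias is likely, but it is not assured.

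**Step 4: fever.** The No rule excludes fever. With no daily records, both answers leave it missing, so there is no asymmetry.

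**The case against.** The strongest reply is that records missing from the database need not mean a lost diary. The CRB may ask a yes/no question and leave the daily fields empty after No, in which case No with no records is simply how a non-case is stored. The fever exception fits this, because temperature is recorded daily whether or not there is fever (Protocol 9.2.1.3.2). The CRB pages are not in the documents, so neither reading can be proved. On this reading there is no symmetric pool of blank diaries and the table in Step 2 does not apply. The asymmetry and Step 1 still stand, because a Yes with no daily records is still dropped.

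Such subjects should also be rare. Protocol 13.2 has the coordinator clarify missing diary data with the subject and transfer it to the CRB, Protocol 11.1 has site staff interview the subject, and Protocol 9.2.1.3 has reactions asked about at each visit. One graded day is enough to bring the subject back. This limits the number but leaves the rule as it is: a subject may recall having had pain without recalling any day's grade.

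Three stronger readings are tempting, and the documents do not support them.

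- *All solicited rates are biased downward.* Steps 3 and 4 rule this out for size-based reactions and fever.
- *The difference between vaccine groups is narrowed.* The formula in Step 2 has slope (1 − m)/(1 − mp)², which at m = 10% exceeds 1 above a rate of about 51%. At m = 10%, a true 80% against 60% is reported as 0.72/0.92 = 78.3% against 0.54/0.94 = 57.4%, a gap of 20.8 points instead of 20. Equal m in both groups is also an assumption.
- *The No rule should be withdrawn for size-based reactions.* If No leaves the daily fields empty, this deletes real non-cases. With 10 events in 100 subjects and half of the 90 non-cases blank, the rate becomes 10/55 = 18% instead of 10%.

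**Conclusion.** The point holds for the five subjectively graded reactions. The SAP uses the investigator's answer in one direction only, and the reported rate is at or below the rate that uses both answers. The outcome for Yes is not written out. It follows from the absence of any step for it, together with SAP 4.4.1.1.3.

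Under the Step 2 assumptions the bias at a true 40% is about −0.2 to −0.5 points for 1% to 2% blank and −1.2 points for 5% blank. These are well inside the confidence half-widths shown, and the blank share is an assumption throughout. For size-based reactions the direction is open, and no general claim is made about the difference between vaccine groups.

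Safety is descriptive with no hypotheses tested (SAP 5.1.2.2.1), and the primary immunogenicity conclusion is untouched. This is a cheap improvement, worth making because exclusion that depends on the outcome is hard to defend and easy to remove.

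**What to change.** In SAP 4.4.1.1.1 and 4.4.1.1.3:

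- Keep the No rule as it stands.
- For pain, headache, malaise, myalgia and shivering, state that an investigator answer of Yes with all daily records missing counts as an occurrence with maximum intensity Missing, and that the subject stays in numerator and denominator.
- For erythema, swelling, induration and bruising, leave the main table unchanged. Add a sensitivity row that counts such a Yes as an occurrence, with the number of affected subjects by vaccine group.

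The cost is a short SAP addition and a small change to the derivation program before the first database lock. The downside is slightly higher reported rates and a missing-intensity row in some tables.

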4.4.1.1.2 Maximum Intensity

Maximum intensity is derived from the daily intensities computed as described in [Section 4.4.1.1.1](#) and is calculated as the maximum of the daily intensities over the period considered.

The Grade of intensity is applied following the rules described in the Section 9.2.1.3.2 of the protocol.

4.4.1.1.3 Occurrence

Occurrence is derived from the maximum intensity on the period considered:

- None: No occurrence
- Grade 1, Grade 2, or Grade 3: Occurrence
- Missing: Missing occurrence

Subjects with at least one non-missing occurrence for a specific endpoint will be included in the analysis. Conversely, those without a non-missing occurrence will not be included in the analysis of the endpoint.

4.4.1.1.4 Time of Onset

Time of onset is derived from the daily intensities computed as described in [Section 4.4.1.1.1](#). It corresponds to the first day with intensity of Grade 1, Grade 2, or Grade 3.

Note: If a reaction is not continuous (ie, reaction occurs over 2 separate periods of time intervened by at least one daily intensity Missing or None) then the time of onset is the first day of the first occurrence.

Table 4.1: Categories for time of onset

Injection Site Reactions (D0-D7)	Systemic Reactions (D0-D7)
D0-D3	D0-D3
D4-D7	D4-D7

4.4.1.1.5 Number of Days of Occurrence

Number of days of occurrence over the period considered is derived from the daily intensities computed as described in [Section 4.4.1.1.1](#). It corresponds to the number of days with daily intensities of Grade 1, Grade 2, or Grade 3. Number of days of occurrence on the solicited period with a specified intensity may also be derived.

Table 4.2: Categories for number of days of occurrence during the solicited period

Injection Site Reactions (D0-D7)	Systemic Reactions (D0-D7)
1-3 days	1-3 days
4-7 days	4-7 days
8 days	8 days

4.4.1.1.6 Overall Number of Days of Occurrence

If a reaction is ongoing at the end of the solicited period, then the overall number of days of occurrence is derived from the daily intensities and the stop date of the reaction after the end of the solicited period. The overall number of days of occurrence is:

- $(\text{stop date} - \text{vaccination date}) + (\text{number of days of occurrence within the solicited period}) - \text{length of the solicited period} + 1$.

If the stop date is missing or incomplete (containing missing data [MD]), the overall number of days of occurrence will be considered as Missing.

Table 4.3: Categories for overall number of days of occurrence

Injection Site Reactions	Systemic Reactions
1-3 days	1-3 days
4-7 days	4-7 days
≥ 8 days	≥ 8 days
Missing	Missing

4.4.1.1.7 Ongoing

Ongoing is derived from the last daily intensity of the solicited period computed as described in [Section 4.4.1.1.1](#) and the maximum intensity on the ongoing period. The investigator's ongoing flag is not used because the measurement would determine the ongoing status of the reaction.

Note: a reaction could be derived as not ongoing for the analysis despite being considered as ongoing by the investigator (eg, when the maximum measurement after D7 is > 0 mm but < 25 mm). If the last daily intensity of the solicited period is at least Grade 1 and maximum intensity on the ongoing period is also at least Grade 1, then the reaction is considered ongoing. In any other cases the reaction will not be considered as ongoing.

4.4.1.2 Unsolicited AEs

4.4.1.2.1 Occurrence

An observation will be considered an event if it has at least a verbatim term and is not a Grade 0 intensity event. Grade 0 events should be included in the listing "Unsolicited (non-serious) adverse events not included in the safety analysis."

4.4.1.2.2 Intensity

Intensity for unsolicited AEs will be derived according to the following classification: None, Grade 1, Grade 2, Grade 3, or Missing.

If the unsolicited AE is measurable and its preferred term is part of the list of solicited reactions, then the measurement is derived based upon and following the same rule than the intensity scales defined in the protocol for that measurable injection site or systemic reaction.

Note the intensity could be considered "None" (not a reaction) in the analysis despite being considered a reaction by the investigator (eg, swelling measurement > 0 mm but < 25 mm in adults). Intensity for the other unsolicited non-serious AEs will correspond to the value reported in the electronic case report form (eCRF).

The maximum intensity corresponds to the highest intensity for a unique term.

4.4.1.2.3 Time of Onset

Time of onset is derived from the start date of the unsolicited AE provided in the clinical database and the date of last vaccination:

- Start date of the unsolicited AE – date of vaccination.

The time of onset should be considered as missing only if one or both of the dates are missing or partially missing.

The unsolicited non-serious AEs will be analyzed “Within 28 days”, which corresponds to AEs with a time of onset between 0 and 28 days after vaccination or missing. An AE with missing time of onset will be considered to have occurred just after the vaccination indicated by the visit number, so will be included in these tables.

Note: Unsolicited AEs that occurred before vaccination (negative time of onset) or with a time of onset higher than defined above (> 28 days) will not be included in analysis, but will be listed separately.

Time of onset will be displayed as follows:

- D0-D3
- D4-D7
- D8-D14
- \geq D15
- Missing

SAEs will be analyzed throughout the study using the following periods:

- During post-Dose period (ie, within 28 days after the injection)
- During the 6-month follow-up period (ie, from 29 days after the injection until the last subject contact)
- During the study (ie, all SAEs that occurred during the study)

An SAE with missing time of onset will be considered to have occurred just after the vaccination indicated by the visit number, so will be included in these tables.

4.4.1.2.4 Duration

Duration is derived from the start and stop dates of the unsolicited AE provided in the clinical database:

- Stop date of unsolicited AE - start date of unsolicited AE + 1.

The duration should be considered as missing only if one or both of the start and stop dates of the unsolicited AE is missing or partially missing.

Duration will be displayed by period as following:

- 1-3 days
- 4-7 days
- 8-14 days
- \geq 15 days
- Missing

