- § Collection of the first blood sample (BL0001) is to occur before vaccination.
- \*\* Subjects will use this diary card to record information about solicited reactions from D0 to D7, as well as unsolicited AEs, SAEs, and AESIs from D0 to V02 after vaccination.
- †† Staff will collect the diary card at V02, and review any solicited reactions ongoing at V02, unsolicited AEs, concomitant medications, SAEs, and AESIs.
- ‡‡ Subjects will use this memory aid to collect information on SAEs and AESIs from V02 to the D180 Safety Follow-up Call.
- §§ During the D180 telephone call, staff will review the memory aid to identify the occurrence of any SAEs and AESIs that had not yet been reported.
- \*\*\* AESIs will have the same detailed information collected as SAEs. These include new onset of Guillain-Barré Syndrome (GBS), encephalitis/myelitis (including transverse myelitis), Bell's Palsy, optic neuritis, and brachial neuritis.

Abbreviations: AE, adverse event; AESI, adverse event of special interest; BL, blood sampling; D, day; DC, diary card; FDA, Food and Drug Administration; GBS, Guillain-Barré Syndrome; ICF, informed consent form; SAE, serious adverse event; US, United States; V, visit.

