**9.2.1.3.3 Unsolicited Adverse Events**

In addition to recording solicited reactions, subjects will be instructed to record any other medical events that may occur during the 28-day period after vaccination. Space will be provided in the DC for this purpose.

Information on SAEs will be collected and assessed throughout the study, from inclusion until 6 months after vaccination. Any SAE occurring at any time during the study will be reported by the Investigator in the CRB according to the completion instructions provided by the Sponsor; this includes checking the “Serious” box on the AE CRF and completing the appropriate Safety Complementary Information CRFs. All information concerning the SAE is to be reported either as part of the initial reporting or during follow-up reporting if relevant information became available later (eg, outcome, medical history, results of investigations, copy of hospitalization reports). See [Section 10](#) for further details on SAE reporting.

For each unsolicited AE (whether serious or non-serious), the following information is to be recorded:

- Start and stop datesa
- Intensity of the event:

For measurable unsolicited AEs that are part of the list of solicited reactions, the size of the AE as well as the temperature for fever will be collected and analyzed based on the corresponding scale used for solicited reactions (see [Table 9.1](#) and [Table 9.2](#)).

All other unsolicited AEs will be classified according to the following intensity scale:

- Grade 1: A type of AE that is usually transient and may require only minimal treatment or therapeutic intervention. The event does not generally interfere with usual activities of daily living.
- Grade 2: A type of AE that is usually alleviated with additional therapeutic intervention. The event interferes with usual activities of daily living, causing discomfort but poses no significant or permanent risk of harm to the research participant.

---

a The stop date of all related AEs will be actively solicited. For other events, the investigator will provide the stop date when it becomes available. AEs for which no stop date was obtained during the course of the study will be considered as ongoing at the end of the study.

- Grade 3: A type of AE that interrupts usual activities of daily living, or significantly affects clinical status, or may require intensive therapeutic intervention.

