5.3.1.5 Start Date and Stop Date

Missing or partially missing start dates for unsolicited AEs will remain missing and not be imputed. If either the start or stop date is missing or partially missing, the time of onset will be considered to be missing. Nevertheless unsolicited AEs with missing time of onset will be included in analyses according to the visit collected.

Missing or partially missing stop dates for AEs (solicited reactions and unsolicited AEs) will remain missing and not be imputed.

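### The SAP sets duration to 'Missing' whenever the stop date is absent, so events that did not end are pooled with events of unknown dates and the longest-duration rows are understated

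*SAP*

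**What the plan says.** For unsolicited AEs, SAP 4.4.1.2.4 defines duration as "Stop date of unsolicited AE - start date of unsolicited AE + 1" and adds: "The duration should be considered as missing only if one or both of the start and stop dates of the unsolicited AE is missing" or incomplete. The display categories are 1-3, 4-7, 8-14 and ≥ 15 days, plus 'Missing'.

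For a solicited reaction that continues after D7, SAP 4.4.1.1.6 uses the stop date to add the later days to those in the diary period. It then says: "If the stop date is missing or incomplete (containing missing data [MD]), the overall number of days of occurrence will be considered as Missing". The categories shown in Table 4.3 are 1-3, 4-7 and ≥ 8 days, plus 'Missing'.

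SAP 5.3.1.5 rules out a substitute date: "Missing or partially missing stop dates for AEs (solicited reactions and unsolicited AEs) will remain missing and not be imputed". Neither display has a row for ongoing events.

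The protocol gives the empty field a meaning. Section 9.2.1.3.3, footnote a, says: "AEs for which no stop date was obtained during the course of the study will be considered as ongoing at the end of the study". Under the same footnote, stop dates are actively sought only for related AEs; for other events the investigator supplies one if it becomes available. At V02 (D28 to D35), staff collect the diary card and "review any solicited reactions ongoing at V02", along with unsolicited AEs (Table of Study Procedures, footnote).

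**The concern.** Duration of unsolicited AEs is a named secondary safety endpoint (Protocol 9.2.1.2). The longer an event lasts, the more likely it is to be open when its status is last recorded, and so to have no stop date. The missingness therefore depends on the quantity being summarised, and it works in one direction: events leave the top category and the distribution looks shorter than it was.

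A reader of the table cannot tell an AE that never resolved from one whose dates were not recorded. Little else in the plan recovers this. Among the items recorded for each unsolicited AE (Protocol 9.2.1.3.3), outcome is listed only for SAEs, so for a non-serious AE the empty stop date is the listed sign that it was ongoing. The derived 'Ongoing' variable in SAP 4.4.1.1.7 applies to solicited reactions and means persistence past D7, not open at last contact.

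**Working it through.** The plan states no figure to reproduce, so the check applies the SAP's own formulas to events that have no stop date.

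**Formula check.** SAP 4.4.1.1.6: (stop − vaccination) + n − 8 + 1, where n is the number of days at Grade 1 or above within D0-D7 and 8 is the length of that period. Onset D0 and stop D10 gives 10 + 8 − 8 + 1 = 11 days, as it should.

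**Unsolicited AEs.** Inputs: onset day o from D0 to D28 (SAP 4.4.1.2.3), and c, the last day on which the AE was documented as present. Minimum duration = c − o + 1.
- c = D28 (earliest V02): 28 − 14 + 1 = 15, so every onset from D0 to D14 (15 of 29 onset days) already belongs in '≥ 15 days'. Onsets D15 to D28 give minima of 14 down to 1 day, and the category stays open.
- c = D35 (latest V02): 35 − 21 + 1 = 15, so onsets D0 to D21 (22 of 29) qualify.
- c = D180: minima run from 180 − 28 + 1 = 153 to 181 days, so all qualify. The D180 call reviews SAEs and AESIs (Protocol 5.1.4), so this case applies only to events whose status was recorded there.

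The SAP rule shows all of these as 'Missing' if the stop date is absent.

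**Solicited reactions.** SAP 4.4.1.1.7 derives a reaction as ongoing when it is at least Grade 1 on the last diary day and its maximum intensity after D7 is also at least Grade 1. At least one graded day after D7 is then certain. Taking D8, the earliest possible day, as the last day: 8 + n − 8 + 1 = n + 1.
- n = 8 gives at least 9 days; n = 7 gives at least 8. Both belong in '≥ 8 days'.
- n ≤ 6 gives a minimum of 7 or less, and the category stays open.

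So a reaction graded on all 8 diary days is '8 days' in Table 4.2. If it continues without a stop date it is 'Missing' in Table 4.3, although '≥ 8 days' is certain.

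**Possible size (assumed inputs).** The documents give no frequencies. Let t be the true share of unsolicited AEs lasting 15 days or more, and m the share of those with no stop date. Per 100 AEs, the '≥ 15 days' row shows 100·t·(1 − m), and 100·t·m move to 'Missing'. For t of 10-30% and m of 10-50%:
- the row shows between 100 × 0.10 × 0.50 = 5 and 100 × 0.30 × 0.90 = 27, against true values of 10 to 30;
- between 100 × 0.10 × 0.10 = 1 and 100 × 0.30 × 0.50 = 15 move to 'Missing'.

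**The case against.** The rule is deliberate and visible. Protocol 12.3.1 says that missing safety data will not be replaced, and the SAP applies this to stop dates. The events stay in the occurrence analyses and in a displayed 'Missing' row, SAE outcome is at least listed (SAP 4.4.1.2.6), and no safety hypothesis is tested. All of this stands and limits the weight of the point. It does not answer it: placing an event in an open-ended category on a documented minimum imputes no stop date, and the 'Missing' row does not separate ongoing from unknown.

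The safeguards for related events also stand. Solicited reactions and all injection-site AEs are related by convention, related AEs have their stop dates sought, and for those that persist the investigator reports a date of disappearance or of chronicity (Protocol 9.2.1.3.6). The documents do not say whether a chronicity date fills the stop-date field, and the SAP has no rule for it.

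A reader might infer more than the documents support:
- *That the solicited-reaction endpoint as a whole is distorted.* The endpoint concerns reactions up to 7 days after vaccination. Table 4.2 matches it most directly and uses daily intensities, not stop dates. Only the additional overall count in Table 4.3 is touched. The two tables measure different quantities, so '8 days' beside 'Missing' is not a contradiction.
- *That any solicited reaction ongoing at V02 has lasted at least 22 days.* Putting D28 into the formula gives 28 + n − 8 + 1 = 21 + n, but this assumes Grade 1 or above through V02. The SAP sets aside the investigator's ongoing flag and uses the maximum intensity after D7. A swelling of 25 mm on D7 and D8 and 10 mm at V02 may be ongoing to the investigator, yet is not known to be graded for 22 days.
- *That persistent injection-site reactions are affected most.* The convention on relatedness points the other way.
- *That the correct category is known in most cases.* No frequency is given. The protocol's ongoing status is a default for an empty field, not an observation, and the listed AE items include no date last seen.

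**Conclusion.** The point holds for the duration of unsolicited AEs and, more narrowly, for the overall days of occurrence of solicited reactions. The SAP does not carry over the protocol's reading of an absent stop date, and it withholds a top category that is sometimes certain from recorded data. The most exposed group is unrelated unsolicited AEs, including new chronic conditions.

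The direction of the error is clear; its frequency cannot be derived. The conclusion assumes a complete start date, documented presence at V02 or a later contact that recorded status (or, for solicited reactions, a graded record after D7), and a stop-date field that is left empty for such events. A reader might infer that these events vanish from the safety analysis. They do not: they lose their duration category only, in a descriptive summary, and the immunogenicity conclusions are unaffected. The change should still be made, because the rule biases the summary of a named endpoint in one direction and is cheap to correct.

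**What to change.** Amend SAP 4.4.1.2.4 and 4.4.1.1.6, with a matching sentence in 5.3.1.5:

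(a) Unsolicited AEs. If the start date is complete, the stop date is absent, and the AE was documented as present at V02 or at a later contact that recorded its status, compute the minimum duration to that date. Count it as '≥ 15 days' when the minimum reaches 15, for example with onset D0-D14 and presence at D28.

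(b) Solicited reactions. If 4.4.1.1.7 derives the reaction as ongoing after D7 and there is no stop date, take the days at Grade 1 or above in the diary period plus one day as the minimum. Count it as '≥ 8 days' when reached, for example with all 8 diary days graded. Do not assume Grade 1 or above through V02.

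(c) Otherwise show 'Ongoing, duration not complete' as its own row, and keep 'Missing' for an unknown start date or unknown status. State whether the protocol's footnote convention alone, without a recorded status, is enough for the ongoing row.

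The cost is SAP wording, one more display row and minor programming. Part (a) also depends on status at V02 being recorded, because the listed AE items contain no date last seen.
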